7.7.1 Cost data collection

Data collection will be undertaken prospectively at all units participating in the trial. The process of collecting resource use data will be undertaken separately from data collection on unit costs.

The main resource use to be monitored includes the following:

- 1) The duration of health service staff time spent carrying out IOCS procedure including staff training
- 2) Equipment and disposables required for the IOCS procedure.
- 3) Number of donor blood transfused units required by participants,
- 4) Length and type of hospital inpatient stay (Any adverse events will increase the length and type of hospital stay)

Unit costs will be obtained and attached to resource items in order that a cost can be calculated for each caesarean section. Unit costs will be obtained from published sources and centres participating in the trial. Published sources will include Unit Costs of Health and Social Care (30) and NHS Reference cost. Costs used in other relevant published sources will be sought for use in sensitivity analysis.

7.7.2 Analysis

Given the objective of the trial and the duration of follow up, only a within trial economic analysis will be carried out. A preliminary cost consequence analysis will compare all costs and outcomes for the intervention and current practice in a disaggregated format. The main economic analysis will be in the form of a cost effectiveness analysis based on the outcome of cost per donor blood transfusion avoided.

The analysis will adopt an incremental approach in that data collection will concentrate on resource use and outcome differences between trial arms. As the majority of cost data are skewed, and the mean cost of each procedure is of importance, a bootstrapping approach will be undertaken in order to calculate confidence intervals around the mean costs. The recommended approach to discounting will be followed if necessary, which would include discounting costs and benefits as per NICE guidelines at 3.5%. But as the trial and analysis are limited to the immediate post natal period, and therefore not likely to extend beyond 12 months, this process is not likely to be necessary.

If appropriate, we will present results of all economic analyses using cost-effectiveness acceptability curves to reflect sampling variation and uncertainties in the appropriate threshold cost-effectiveness value where appropriate. Uncertainty in the confidence to be placed on the results of the economic analysis will be explored by estimating. These plot the probability that the intervention is cost effective against threshold values for cost effectiveness. The robustness of the results will be explored using sensitivity analysis. This will explore uncertainties in the trial based data itself, the methods employed to analyse the data and the generalisability of the results to other settings.

8 Data Handling & Record Keeping

8.1 Confidentiality

The Chief Investigator is the ‘Custodian’ of the data and will ensure that information with regards to study participants will be kept confidential and managed in accordance with the Data Protection Act, NHS Caldicott Guardian, The Research Governance Framework for Health and Social Care and Research Ethics Committee Approval.

Identifiable information to be collected from the participants include, full name, DOB and hospital number and contact details at screening. This information will be used to contact participants but will not leave the study site. All case report forms will be pseudonymised.

The trial data will be made available to suitably qualified members of the research team, study monitors and auditors, the REC and regulatory authorities as far as required by law.

The participants will be anonymised with regards to any future publications relating to this study.

8.2 Required Study Documents

- A signed protocol and any subsequent amendments
- PCTU self-monitoring template for the trial team to complete on a regular basis as detailed by the Trial Monitoring section
- Current/Superseded Patient Information Sheets (as applicable)
- Current/Superseded Consent Forms (as applicable)
- Indemnity documentation from sponsor
- Conditions of Sponsorship from sponsor
- Conditional/Final R&D Approval
- Signed site agreements
- Ethics submissions/approvals/correspondence
- CVs of CI and site staff
- Laboratory accreditation letter, certification and normal ranges for all laboratories to be utilised in the study
- Delegation log
- Staff training log
- Site signature log
- Identification log
- Enrolment log
- Monitoring visit log
- Protocol training log
- Correspondence relating to the trial
- Communication Plan between the CI/PI and members of the study team

- SAE reporting plan for the study

8.3 Case Report Forms

For all participating women, pre-operative trial data will be recorded in the maternity notes which will be completed by the attending obstetrician, anaesthetist or midwife. The following data will be abstracted from the notes and recorded on CRF for the trial, relying on CLRN research support in each of the recruiting hospitals.

Pre-Operative

- Demographic data
- Obstetric history
- Gestational Age/Prognostic factors/Indication for CS
- Pre-op Hb level

Intra/Post-Operative

- AE/SAE Log

Further information will be collected during intra-operative and post-operative phase and at the time of discharge from hospital. This data will be recorded directly to trial CRF's by the attending obstetrician, anaesthetist or midwife as outlined on the trial delegation log. Any missing information will be obtained from trial participant prior to discharge. Checking of this data, along with administration of multidimensional fatigue inventory on the post natal wards, will rely on CLRN research support in each of the recruiting hospitals. No further routine follow up will be required after discharge.

The following trial specific data which will be entered directly to CRF:

Pre-Operative

- Eligibility criteria checklist

Intra-Operative

- Transfusion of ≥ 1 unit donor blood
- Number of donor blood units transfused
- Volume of blood returned by IOCS
- IOCS consumables used
- IOCS technical failure
- Maternal exposure to fetal blood

Post-Operative

- Transfusion of ≥ 1 unit donor blood
- Number of donor blood units transfused
- Hb level
- Transfusion reaction
- Anti D requirement and dose
- Time to first mobilisation after CS

Discharge

- Multidimensional Fatigue Inventory (MFI)
- Length of stay in Hospital

Other

- Additional Information/Note to File CRF
- Final Study Status /Early Withdrawal CRF

Suitably qualified members of the study team, as documented on the trial delegation log will be responsible for the completion of the CRFs. CRFs will be pseudonymised using a participant code allocated at time of randomisation. The number will be generated by the online randomisation system and recorded on the Randomisation Form. This code will consist of the trial site code followed by the consecutive recruitment number starting at 001. Site codes are documented in Appendix 4.

E.g.: Royal London Hospital (01), participant number 1 (001) : 01001

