1.3.7 Survey of women delivered by Caesarean Section

A survey of women undergoing CS in whom IOCS was used for anticipated haemorrhage was conducted at Sheffield Teaching Hospital, one of the co-applicant centres. The majority of CSs were performed "awake" under regional anaesthesia for enhanced maternal and fetal safety. The opinions of the recipients of IOCS in CS are therefore particularly pertinent to inform any proposed study advocating its routine use.

Women scheduled for CS were given written and verbal information about IOCS prior to operation. A self-administered questionnaire was employed in the immediate postnatal period. Of 71 women surveyed, 69 completed and returned the questionnaire, a response rate of 97%. The responses in Figure 1 confirm that women were reassured by the prospect that IOCS could re-transfuse their own blood and perceived the technology as lower risk than donor blood transfusion. Twenty two women went on to have IOCS with 16 (72%) receiving salvaged blood. Of these 22 women, 17 (77%) expressed a preference for IOCS to be made available in the event of them requiring a CS in the future.

The results of the survey (Figure 1) demonstrate that the attitude to IOCS during CS in women is very positive and that they regard the technology as reassuring and safe.

[figure not shown]
Figure 1: Women’s responses

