1.3.9 Audit of transfusion rates in Caesarean Section

A detailed audit of donor blood use at the Royal Hallamshire Hospital Sheffield 2009-10, without IOCS in routine use, was performed by cross-reference of perioperative records, blood bank data and electronic records stored in cell salvage machines. It reported that in a recent series of 1647 CS over 10 months, 89 women were transfused with donor blood, giving a rate of 5.4% ([name], Personal communication). A similar audit at Birmingham Women's Hospital of all CS carried out in 2006, showed that of 1674 women, 83 (5.0%) received a transfusion, with a mean transfusion volume of 1620ml SD 1350ml (1). This equates to 3.6 +/- 3 units of donor blood administered. Both auditing units deliver approximately 7300 women per year with a similar CS rate and can be considered representative of UK tertiary obstetric unit practice.

It is important to note that these data include both acute transfusion at operation and any donor blood given in the postoperative period to treat symptomatic anaemia before hospital discharge. Our study population is defined by women undergoing CS who have at least one identifiable risk factor for haemorrhage. We have defined 'Increased risk of haemorrhage' to include elective CS for abnormal placentation and previous CS and all emergency CSs. The emergency CS group includes a number of indications which are at particularly high risk of haemorrhage including antepartum haemorrhage and pre-eclampsia. The baseline transfusion requirement of this selected population is likely to be elevated. For example, a recently published study of 246 Caesarean deliveries for placenta praevia reported 29% of cases required transfusion. Of those women who received donor blood, 63% required 3 units or more (23).

2 Trial Objectives and Design

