7.1 Trial Outcomes

7.1.1 Primary outcome

The primary outcome is the proportion of women needing donor blood transfusion to deal with haemorrhage and its consequences. (see section 3.5).

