8.4 Data collection, processing and monitoring

All trial data will be managed according to the PCTU data management SOP's.

Data will be;

- Collected using case report forms as outlined in section 8.3.
- Verified and processed on site by trial coordinators or other delegated members of the study team for data entry to the trial database.
- Monitored centrally for consistency, viability and quality by the PCTU.
- Screened for out-of-range data, with cross-checks for conflicting data within and between CRF using computerised logic checking screens
- Referred back to the relevant centre for clarification in the event of missing items or uncertainty

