8.7 Quality Control and Quality Assurance

8.7.1 Summary Monitoring Plan

The study sites will perform remote trial monitoring according to the agreed PCTU trial monitoring plan and self-monitoring template. The frequency and intensity will be determined by the PCTU monitoring plan and risk assessment. Trial monitoring will include source data verification checks on informed consent forms and eligibility for randomisation and a sample set of CRFs. The remote

monitoring reports reviewed by the PCTU and all findings will be followed up and actioned as per the trial monitoring plan.

The study sites will return self-monitoring templates to the PCTU every six months. The PCTU will also carry out triggered audits as determined by risk assessment or through findings identified via the remote monitoring reports. A random sample of cases will be monitored at source when site visits are performed. The documents to be verified will be randomly selected. Any major discrepancies found at a site visit would trigger a more extensive audit of trial data at the site involved. In addition, the sponsor may also carry out an audit throughout the duration of the trial.

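### Section 8.3 has missing donor-transfusion items, including the primary outcome, filled in from the woman's own account, and the resulting error can differ between arms

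*Protocol*

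**What the plan says.** Protocol section 7.1.1 defines the endpoint: "The primary outcome is the proportion of women needing donor blood transfusion to deal with haemorrhage and its consequences". Section 8.3 describes how the data are obtained. Pre-operative data are abstracted from the maternity notes. For the rest, "Further information will be collected during intra-operative and post-operative phase and at the time of discharge from hospital", and these data are entered straight onto the CRF by the attending obstetrician, anaesthetist or midwife. The next sentence is the rule at issue: "Any missing information will be obtained from trial participant prior to discharge".

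The list of directly entered items that follows has "Transfusion of ≥ 1 unit donor blood" under both the intra-operative and the post-operative phase, with the number of donor units beside it each time. Section 8.3 exempts no item from the rule and names no record from which a missing transfusion item should be taken.

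Three other places bear on this:

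- Section 8.4 has missing or uncertain items "Referred back to the relevant centre for clarification in the event of missing items or uncertainty", but says that data are collected as section 8.3 sets out.
- Section 8.7.1 limits verification: "Trial monitoring will include source data verification checks on informed consent forms and eligibility for randomisation and a sample set of CRFs".
- Section 7.6 analyses the women who have outcome data and treats the remainder as missing at random.

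**The concern.** Read as written, section 8.3 makes recall the source for a missing primary outcome. Most of these operations are done under regional anaesthesia, and some involve heavy bleeding. A woman in that position is a poor witness to whether she received donor units and how many.

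The error need not be equal between arms. By design, salvaged blood goes back to every IOCS woman whose collected volume is sufficient (section 4.6). In the one survey reported, "Twenty two women went on to have IOCS with 16 (72%) receiving salvaged blood". A woman who saw a bag of red cells running may call it a transfusion. In the control arm this particular mistake is possible only in the rare case where IOCS was used there.

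A recalled value also counts as observed data. It therefore escapes both the missing-outcome rule and the sensitivity analyses in section 7.6, and a field that is no longer empty need not prompt a query under section 8.4. The number of units feeds the volume outcome and the cost analysis, so the same weakness reaches those.

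**Working it through.** **Plan's own figure.** Inputs from section 7.5: 5% control, 3% IOCS, two-sided 5% test, 80% power. With pooled variance under the null and no continuity correction,

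n per arm = [1.96 × √(2 × 0.04 × 0.96) + 0.842 × √(0.05 × 0.95 + 0.03 × 0.97)]² / 0.02² = 1,506.

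The total is 3,012, as in the protocol's table. Adding the 38 women allowed for loss gives 3,050. Power at 1,525 per arm is 80.5%.

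**Planned gap in events.** 1,525 × 0.05 = 76.25 and 1,525 × 0.03 = 45.75, a gap of 30.5. Each false IOCS-arm event removes 1/30.5, or about 3%, of it.

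**Model for salvaged blood reported as donor blood.** Observed IOCS rate = 0.03 + 0.97 × m × r × e, with control held at 5%.

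- m is the share of IOCS women whose transfusion field is filled from recall. The documents give no value. I assume 38/3,050 = 1.25%, the loss allowance in section 7.5, which is about 19 IOCS women.
- r is the share given salvaged blood. I take 72% from the survey in section 1.3.7, and 40% as an assumed lower value, because the survey is 22 women at one centre who had IOCS for anticipated haemorrhage.
- e is the share of those women who report donor blood wrongly. This is an assumption throughout.

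For e = 10% and r = 72%: 0.97 × 0.0125 × 0.72 × 0.10 = 0.00087, and × 1,525 gives 1.3 false events.

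| r | e | False IOCS events | Observed IOCS rate | RR | Power |
|---|---|---|---|---|---|
| any | 0% | 0 | 3.00% | 0.60 | 80.5% |
| 72% | 10% | 1.3 | 3.09% | 0.62 | 76% |
| 72% | 25% | 3.3 | 3.22% | 0.64 | 70% |
| 72% | 50% | 6.7 | 3.44% | 0.69 | 57% |
| 40% | 10% | 0.7 | 3.05% | 0.61 | 78% |
| 40% | 25% | 1.9 | 3.12% | 0.62 | 75% |
| 40% | 50% | 3.7 | 3.24% | 0.65 | 69% |

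If m = 0, as in the pilot (section 1.3.6, primary endpoint collected for every woman), the first row applies.

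**The reverse error.** The model leaves out true donor transfusions that are forgotten or taken for salvaged blood. If gaps are unrelated to bleeding, the recalled fields hold about 45.75 × 0.0125 = 0.6 true events in the IOCS arm and 76.25 × 0.0125 = 1.0 in the control arm, so little can be lost. If gaps cluster in emergencies with heavy bleeding, more true events sit in the recalled fields and the losses could be larger in either arm. The documents do not say which applies.

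**The case against.** The strongest reply is that the sentence is loose wording and not a working rule. The same list holds IOCS volume, consumables, technical failure and haemoglobin. No woman could supply these, and section 5.6 has haemoglobin and Kleihauer results transcribed from pathology reports. There are also real safeguards. Network research staff check the data (8.3). Coordinators verify them on site, and logic checks look for conflicts within and between CRFs (8.4). Haemoglobin is recorded before and after a donor transfusion (4.4), so a salvaged bag reported as donor blood could stand out. The protocol expects virtually complete primary-outcome data.

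Much of this stands, and it keeps the likely effect small. It does not remove the rule. No safeguard names the record against which a transfusion item is to be checked, CRF verification is by sample, and section 8.4 points back to section 8.3 for how data are collected.

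Two stronger readings are tempting, and the documents support neither:

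- **False events arise in the IOCS arm alone.** Sections 3.5 and 4.6 allow IOCS in control women, and the pilot had one such case. Misreporting is a risk here, not a stated fact, and the reverse error is possible.
- **The trial measures its endpoint less well than its planning rate was measured.** The planning rate is 5%, from contemporary reports and two audits (5.4% and 5.0%). Only the 5.4% audit is described as "performed by cross-reference of perioperative records, blood bank data and electronic records stored in cell salvage machines". That shows a record-based source was known and usable; it does not show a general mismatch.

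**Conclusion.** The point holds as a defect in a stated rule with a small likely effect. Following section 8.3 can put unreliable values into the primary outcome, by a mechanism that falls almost wholly on the IOCS arm. Salvaged blood reported as donor blood would bias against IOCS; the net direction of all recall errors is not established.

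The size runs from nothing at complete data to about 1 to 7 false events against a gap of about 30, with power between 76% and 57%, on the assumed 1.25% recall share, 72% return and 10% to 50% misreporting. A reader might infer a severe loss of power. For example, a 5% recall share with 72% return and 25% misreporting gives 13.3 false events and power of about 33%. That needs about 76 IOCS women (0.05 × 1,525) with a missing transfusion field filled from recall, which is well beyond the protocol's expectation of about 1% loss. This is a cheap improvement worth making, not evidence that the trial's result would be wrong.

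**What to change.** Amend section 8.3 and bring section 8.4 into line with it:

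- Missing or inconsistent entries for donor transfusion (yes/no) and number of donor units are taken from the hospital transfusion or blood-bank record for the admission.
- A missing volume returned by IOCS is taken from the cell-salvage record.
- Information from the participant is limited to items only she can give, such as the MFI.
- Section 8.4 states that centre queries on transfusion items are answered from those same records.

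The cost is a short change of text and CRF instruction, plus a record look-up by the research staff who already check these data. The look-up can be limited to women with missing or inconsistent items. Sample size and analysis do not change.

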8.4 Data collection, processing and monitoring

All trial data will be managed according to the PCTU data management SOP's.

Data will be;

- Collected using case report forms as outlined in section 8.3.
- Verified and processed on site by trial coordinators or other delegated members of the study team for data entry to the trial database.
- Monitored centrally for consistency, viability and quality by the PCTU.
- Screened for out-of-range data, with cross-checks for conflicting data within and between CRF using computerised logic checking screens
- Referred back to the relevant centre for clarification in the event of missing items or uncertainty

8.5 Central statistical monitoring

All data will be monitored centrally (at the PCTU) for consistency, viability and quality using bespoke data management systems. Central statistical monitoring will examine patterns of recruitment at sites, characteristics of women, time of recruitment, etc. The trial programmer will run trial-specific programs to extract certain fields from the database (as requested by the Chief Investigator or Trial Statistician) and to cross-check specific information. These fields may include measures of eligibility criteria, management after trial entry and compliance but not by allocation. The trial programmer and Chief Investigator will review the results generated for logic and for any patterns or problems. Outlier data will be investigated. The Chief Investigator and Trial Statistician will decide if any action is required

8.6 Record Retention and Archiving

During the course of research, all records are the responsibility of the Chief Investigator and must be kept in secure conditions. When the trial is complete, it is a requirement of the Research Governance Framework and Trust Policy that the records are kept for a further 20 years. For trials involving BLT Trust patients, undertaken by Trust staff, or sponsored by BLT or QMUL, the approved repository for long-term storage of local records is the Trust Modern Records Centre which is based at [name]. Site files from other sites must be archived at that external site and cannot be stored at the Modern Records Centre.

8.7 Quality Control and Quality Assurance

8.7.1 Summary Monitoring Plan

The study sites will perform remote trial monitoring according to the agreed PCTU trial monitoring plan and self-monitoring template. The frequency and intensity will be determined by the PCTU monitoring plan and risk assessment. Trial monitoring will include source data verification checks on informed consent forms and eligibility for randomisation and a sample set of CRFs. The remote

monitoring reports reviewed by the PCTU and all findings will be followed up and actioned as per the trial monitoring plan.

The study sites will return self-monitoring templates to the PCTU every six months. The PCTU will also carry out triggered audits as determined by risk assessment or through findings identified via the remote monitoring reports. A random sample of cases will be monitored at source when site visits are performed. The documents to be verified will be randomly selected. Any major discrepancies found at a site visit would trigger a more extensive audit of trial data at the site involved. In addition, the sponsor may also carry out an audit throughout the duration of the trial.

